4.2.2 Rationale for the Use of Comparator/Placebo

[figure not shown]
Placebo will be used in this study to allow for an appropriate assessment of the safety data of MK-6194 and to maintain study blinding to reduce bias.

4.3 Justification for Dose

4.3.3 Rationale for Dose Interval and Study Design

Male contraception during clinical studies with MK-6194 is not warranted. Due to the physiology of the testes-blood barrier, the exposure to large protein therapeutics based on immunoglobin scaffolds in the semen is typically limited. In humans, it is estimated that the total concentration of immunoglobulins secreted in semen is 1% of that found in serum [Moldoveanu, Z., et al 2005]. Furthermore, the vaginal exposure to immunoglobulins is estimated to be 10% of that found in semen [Kuo, P. Y., et al 1998] [Sherwood, J. K., et al 1996]. Due to limited risk for genotoxicity and insufficient exposure to ejaculate, large protein therapeutics are not associated with an embryo-fetal risk to female partners.

4.4 Beginning and End-of-Study Definition

08OVCJ

The overall study begins when the first participant (or their legally acceptable representative) provides documented informed consent. The overall study ends when the last participant completes the last study-related contact, withdraws consent, or is lost to follow-up (ie, the participant is unable to be contacted by the investigator).

MK-6194-008-04 FINAL PROTOCOL

Confidential

For purposes of analysis and reporting, the overall study ends when the Sponsor receives the last laboratory result or at the time of final contact with the last participant, whichever comes last.

If the study includes countries in the European Economic Area (EEA), the local start of the study in the EEA is defined as First Site Ready (FSR) in any Member State.

A study may be paused during review of newly available preclinical/clinical safety, PK, pharmacodynamic, efficacy, or biologic data or other items of interest, prior to a final decision on continuation or termination of the study. It may be necessary to keep the study open for gathering/reviewing of additional supportive data to optimally complete the objective(s) of the study. If necessary, the appropriate amendment(s) to the protocol and/or appropriate communication(s) will be generated. If the decision has been made to end the study following this review period, the study end will be defined as the date of the Sponsor decision, and this end of study date supersedes the definitions outlined above. The Competent Authority(ies) and IRB(s)/IEC(s) will be apprised of the maximum duration of the study beyond the last participant out and the justification for keeping the study open.

4.4.1 Clinical Criteria for Early Study Termination

The clinical study may be terminated early if the extent (incidence and/or severity) of emerging effects/clinical endpoints is such that the risk/benefit ratio to the study population as a whole is unacceptable. In addition, further recruitment in the study or at (a) particular study site(s) may be stopped due to insufficient compliance with the protocol, GCP, and/or other applicable regulatory requirements, procedure-related problems or the number of discontinuations for administrative reasons is too high.

A primary objective of this early Phase 1 study is to identify the maximum safe and well-tolerated dose and/or dosing regimen that achieve PK, pharmacodynamic, and/or biologic targets in humans based on preclinical or early clinical data. Therefore, it is possible that study participants may not receive all doses specified in the protocol if this objective is achieved at lesser dose levels in this study. This would not be defined as early termination of the study, but rather an earlier than anticipated achievement of the study objective(s). If a finding (eg, PK, pharmacodynamic, efficacy, biologic targets, etc) from another preclinical or clinical study using the study intervention(s), comparator(s), drug(s) of the same class, or methodology(ies) used in this study results in the study(ies) or program being stopped for nonsafety reasons, this also does not meet the definition of early study termination.

Early study termination is defined as a permanent discontinuation of the study due to unanticipated concerns of safety to the study participants arising from clinical or preclinical studies with the study intervention(s), comparator(s), drug(s) of the same class, or methodology(ies) used in this study.

5 STUDY POPULATION

As stated in the Code of Conduct for Clinical Trials (Appendix 1.1), our studies include people of varying age, race, ethnicity, and sex. The collection and use of these demographic data are to follow all local laws and guidelines in keeping with the needs for participant

MK-6194-008-04 FINAL PROTOCOL 12-DEC-2022

confidentiality while supporting the study of the disease, its related factors, and the IMP under investigation.

Prospective approval of protocol deviations to recruitment and enrollment criteria, also known as protocol waivers or exemptions, is not permitted.

5.1 **Inclusion Criteria**

A participant will be eligible for inclusion in the study if the participant meets all of the following criteria:

Type of Participant and Disease Characteristics

1. Has a clinical diagnosis of atopic dermatitis (as defined by the criteria of Hanifin and Rajka; Appendix 11) for at least 6 months prior to the Screening visit as determined by participant interview to review patient's medical history and confirmation of diagnosis through physical examination by investigator.

2. Participant's disease is of at least moderate severity at the Baseline (Day 1 predose) Visit as defined by the following (see Section 10.12 Appendix 12):

4. Is considered to be a candidate for systemic treatment or phototherapy.

12-DEC-2022 Confidential

08OVCJ

PRODUCT: MK-6194 41

6. Have a Body Mass Index (BMI) ≥ 18 and ≤ 38 kg/m². BMI = weight (kg)/height (m)² at the prestudy (screening) visit. See Section 8.3 for criteria on rounding to the nearest whole number.

Demographics

7. Is male or female, from ≥ 18 years to ≤ 75 years of age inclusive, at the time of providing informed consent.

Female Participants

- 8. A female participant is eligible to participate if she is not pregnant or breastfeeding, and at least one of the following conditions applies:
 - Not a WOCBP

OR

- A WOCBP and:
 - Uses a contraceptive method that is highly effective (with a failure rate of <1%per year), or be abstinent from heterosexual intercourse as their preferred and usual lifestyle (abstinent on a long-term and persistent basis), as described in Appendix 5 during the intervention period and for at least ~84 days after the last dose of study intervention. The investigator should evaluate the potential for contraceptive method failure (ie, noncompliance, recently initiated) in relationship to the first dose of study intervention. Contraceptive use by women should be consistent with local regulations regarding the methods of contraception for those participating in clinical studies.
 - Has a negative highly sensitive pregnancy test (urine or serum as required by local regulations) before the first dose of study intervention. If a urine test cannot be confirmed as negative (eg, an ambiguous result), a serum pregnancy test is required. In such cases, the participant must be excluded from participation if the serum pregnancy result is positive. Additional requirements for pregnancy testing during and after study intervention are in Section 8.3.6.
 - Abstains from breastfeeding during the study intervention period and for at least 84 days after study intervention MK-6194.
 - Medical history, menstrual history, and recent sexual activity has been reviewed by the investigator to decrease the risk for inclusion of a woman with an early undetected pregnancy.

42

Informed Consent

9. The participant (or legally acceptable representative) has provided documented informed consent/assent for the study. Skin biopsy is optional for Panels A-C and it is required for Panels D, E and F.

10. The participant may also provide consent/assent for FBR. However, the participant may participate in the study without participating in FBR.

Additional Categories

- 11. Participant is eligible according to the following TB screening criteria:
 - No evidence of active TB, latent TB, or inadequately treated TB as evidenced by one of the following:
 - Negative QuantiFERON test or equivalent assay at screening or within 90 days prior to randomization date, OR
 - History of fully treated active or latent TB according to local standard of care. Investigator must verify adequate previous anti-TB treatment and provide documentation; these participants do not require QuantiFERON testing.

5.2 **Exclusion Criteria**

The participant must be excluded from the study if the participant meets any of the following criteria:

Medical Conditions

- 1. Has known systemic hypersensitivity to the MK-6194 drug substance or other IL-2 based therapy, its inactive ingredients or the placebo.
- 2. Has a concurrent significant skin disease other than atopic dermatitis (such as psoriasis), a concurrent clinically significant disease or clinically relevant laboratory abnormalities, or a history of any illness or medical condition that, in the opinion of the study investigator or sponsor, might confound the results of the study or poses an additional risk to the patient by their participation in the study.
- 3. Within 6 months prior to Screening, any significant organ dysfunction that is unstable or inadequately treated, including cardiac (see below), renal, liver, central nervous system, pulmonary, vascular, gastrointestinal, endocrine, psychiatric, ophthalmologic, or metabolic conditions or clinically significant laboratory abnormalities that place the patient at unacceptable risk for participation in a trial of an immunomodulatory therapy in the judgment of the investigator and sponsor.
- 4. Mentally or legally incapacitated, has significant emotional problems at the time of prestudy (screening) visit or expected during the conduct of the study or has a history of

clinically significant psychiatric disorder of the last 5 years. Participants who have had situational depression may be enrolled in the study at the discretion of the investigator.

5. History of cancer (malignancy).

Exceptions: (1) Adequately treated nonmelanomatous skin carcinoma or carcinoma in situ of the cervix or; (2) Other malignancies that have been successfully treated with appropriate follow up and therefore unlikely to recur for the duration of the study, in the opinion of the investigator and with agreement of the Sponsor (eg, malignancies that have been successfully treated ≥10 years prior to the screening visit).

- 6. History of myocardial infarction, congestive heart failure (New York Heart Association [NYHA] Class 3 or 4), uncontrolled arrhythmias, cardiac revascularization, stroke, uncontrolled hypertension, or uncontrolled diabetes within 6 months of Screening.
- 7. Has any clinically significant laboratory abnormality, which, in the opinion of the investigator, presents a safety concern to the participant, will prevent the participant from completing the study or will interfere with the interpretation of the study results

- 8. Has a history of moderate to severe pulmonary function test abnormality, which, in the opinion of the investigator, presents a safety concern to the participant.
- 9. Has a history of organ or tissue allograft.
- 10. Has a history of symptomatic herpes zoster within 16 weeks of randomization, or any history of disseminated herpes simplex, disseminated herpes zoster, ophthalmic zoster, or CNS zoster.
- 11. Has active clinically significant infection, or any infection requiring hospitalization or treatment with intravenous anti-infectives up to 8 weeks prior to Day 1 visit, or any infection requiring oral anti-infective therapy up to 6 weeks prior to Day 1 visit.
- 12. Has history of significant multiple and/or severe allergies (eg, drug, latex allergy) or has had an anaphylactic reaction or significant intolerability (ie, systemic allergic reaction) to prescription or nonprescription drugs or food. Participants who have history of severe allergies that do not present a safety concern to the participant may be enrolled in the study at the discretion of the investigator.
- 13. Has positive test(s) for HBsAg, hepatitis C antibodies or HIV, or has positive HBcAb with negative HBsAb serologies.
- 14. Has donated or lost 1 unit of blood (approximately 500 mL) within 4 weeks prior to the prestudy (screening) visit.
- 15. Has had major surgery within 3 months prior to the prestudy (screening) visit or has a major surgery planned during the study.

Prior/Concomitant Therapy

- 17. Has had prior treatment with recombinant IL-2 or modified IL-2 therapy, including MK-6194 (see Section 6.5)
- 18. Is unable to refrain from treatment with topical (except provided low/medium potency topical corticosteroids with hydrocortisone 2.5% cream and triamcinolone acetonide 0.1% cream offered as rescue therapy) prior to week 6 or systemic therapy (including immunosuppressive agents, biologics, corticosteroids, or phototherapy) for atopic dermatitis during the entire trial. Refer to Section 6.5 for other not allowed medication.
- 19. Is unable to refrain from or anticipates the use of any other medication (see Section 6.5), including prescription and nonprescription drugs or herbal remedies beginning approximately 2 weeks (or 5 half-lives) prior to administration of the initial dose of study intervention, throughout the study, until the poststudy visit. There may be certain medications that are permitted (see Section 6.5).
- 20. Has received a live or attenuated virus vaccine within 4 weeks prior to the Screening visit or intends to receive live or attenuated virus vaccination during the course of the study and for 12 weeks after the last dose of study drug.
- 21. Is currently on any chronic systemic (oral or intravenous) anti-infective therapy for chronic infection (such as pneumocystis, cytomegalovirus, herpes zoster, or atypical mycobacteria).
- 22. Is currently receiving lymphocyte depleting therapy.

Prior/Concurrent Clinical Study Experience

23. Is in another investigational study within 4 weeks (or 5 half-lives, whichever is greater) prior to the prestudy (screening) visit. The window will be derived from the date of the last visit in the previous study.

Note:

• Participants in observational studies or non-interventional registry studies may be included in the study.

Diagnostic Assessments

24. Has a QTc interval ≥470 msec (males) or ≥480 msec (females) upon confirmation on recheck at screening or at Predose Day 1 (median), has a history of risk factors for Torsades de Pointes (eg, heart failure/cardiomyopathy or family history of long QT syndrome), has uncorrected hypokalemia or hypomagnesemia, or is taking concomitant medications that prolong the QT/QTc interval.

12-DEC-2022

PROTOCOL/AMENDMENT NO.: 008-04

Other Exclusions

- 25. Under the age of legal consent.
- 26. Is unwilling to comply with the study restrictions (see Section 5.3).
- 27. A regular user of any illicit drugs except cannabis, or has a history of drug (including alcohol) abuse within approximately 1 year. Participants must have a negative UDS, with the exception of cannabis or a medicine for which there is a current prescription from a licensed medical provider, prior to randomization.
- 28. The investigator has any concern regarding safe participation in the study or for any other reason the investigator considers the participant inappropriate for participation in the study.
- 29. Is or has an immediate family member (eg, spouse, parent/legal guardian, sibling, or child) who is investigational site or Sponsor staff directly involved with this study.

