8 STUDY ASSESSMENTS AND PROCEDURES

- Study procedures and their timing are summarized in the SoA.
- Adherence to the study design requirements, including those specified in the SoA, is essential and required for study conduct.
- The investigator is responsible for ensuring that procedures are conducted by appropriately qualified (by education, training, and experience) staff. Delegation of study-site personnel responsibilities will be documented in the Investigator Trial File Binder (or equivalent).
- All study-related medical decisions must be made by an investigator who is a qualified physician.
- All screening evaluations must be completed and reviewed to confirm that potential participants meet all eligibility criteria. The investigator will maintain a screening log to record details of all participants screened and to confirm eligibility or record reasons for screening failure, as applicable.
- Procedures conducted as part of the participant's routine clinical management (eg, blood count) and obtained before signing of ICF may be used for screening or baseline purposes provided the procedure met the protocol-specified criteria and were performed within the time frame defined in the SoA.
- Additional evaluations/testing may be deemed necessary by the investigator and or the Sponsor for reasons related to participant safety. In some cases, such evaluation/testing may be potentially sensitive in nature (eg, HIV, hepatitis C), and thus local regulations may require that additional informed consent be obtained from the participant. In these cases, such evaluations/testing will be performed in accordance with those regulations.

The maximum amount of blood collected from each participant over the duration of the study will not exceed ~524 mL (Appendix 8 OR operations/laboratory manual).

Repeat or unscheduled samples may be taken for safety reasons or for technical issues with the samples.

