- During each treatment administration, if a participant demonstrates a median increase in QTc interval ≥60 msec compared to the median predose baseline measurement, the participant will continue to be monitored by at least single repeat 12-lead ECGs every 15 minutes for at least 1 hour or until the QTc is within 60 msec of baseline. If prolongation of the QTc interval ≥60 msec persists, a consultation with a cardiologist may be appropriate and the Sponsor should be notified.
- During each treatment period, if the median QTc interval is ≥500 msec for postdose measurements, the Sponsor should be notified and the ECGs should be reviewed by a cardiologist. The participant should be telemetry monitored (until the QTc is <500 msec) or should be considered for transfer to a location where closer monitoring and definitive care (eg, a CCU or ICU) is available.

If the participant has unstable hemodynamics, or has any clinically significant dysrhythmias noted on telemetry, the participant should be immediately transferred to an acute care setting for definitive therapy.

If prolongation of the QTc is noted, concomitant medications that prolong QTc should be held until the QTc is within 60 msec of baseline and the QTc is <500 msec.

A cardiologist will be consulted by the investigator as needed to review ECG tracings with significant abnormalities.

8.3.5 **Clinical Safety Laboratory Assessments**

Refer to Appendix 2 for the list of clinical laboratory tests to be performed and to the SoA for the timing and frequency.

- The investigator or medically qualified designee (consistent with local requirements) must review the laboratory report, document this review, and record any clinically relevant changes occurring during the study in the AE section of the CRF. The laboratory reports must be filed with the source documents. Clinically significant abnormal laboratory findings are those which are not associated with the underlying disease, unless judged by the investigator to be more severe than expected for the participant's condition.
- All protocol-required laboratory assessments, as defined in Appendix 2, must be conducted in accordance with the laboratory manual and the SoA.

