10.2 Appendix 2: Clinical Laboratory Tests

- The tests detailed in Table 7 will be performed by the central laboratory.
- Local laboratory results are only required in the event that the central laboratory results are not available in time for either study intervention administration and/or response evaluation. If a local sample is required, it is important that the sample for central analysis is obtained at the same time. Additionally, if the local laboratory results are used to make either a study intervention decision or response evaluation, the results must be entered into the CRF.
- Protocol-specific requirements for inclusion or exclusion of participants are detailed in Section 5 of the protocol.
- Additional tests may be performed at any time during the study as determined necessary by the investigator or required by local regulations.

Table 7 Protocol-required Safety Laboratory Assessments

Laboratory Assessments	Parameters						
Hematology	Platelet Count		RBC Indices:		WBC count with		
	RBC Count		MCV	4CV		Differential:	
	Hemoglobin		MCH		Neutrophils		
	Hematocrit		Reticulocytes		Lymphocytes		
					Monocytes		
					Eosinophils		
					Basophils		
Chemistry	BUN Potass		sium AST/SGOT			Total bilirubin	
						(and direct	
						bilirubin, if total	
						bilirubin is	
						above the ULN)	
	Albumin	Bicar	bonate	Chloride		Phosphorous	
	Creatinine	Sodium		ALT/SGPT		Total Protein	
	Glucose	Calci	um	Alkaline		LDH	
				phosphatase			
	Immunoglobulin E	CRP					
	(IgE)						
Routine Urinalysis	Specific gravity						
	• pH, glucose, protein, blood, ketones, [bilirubin, urobilinogen, nitrite, leukocyte esterase] by dipstick						
	Microscopic examination (if blood or protein is abnormal)						
Pregnancy Testing	Highly sensitive serum or urine hCG pregnancy test (as needed for WOCBP)						

PRODUCT: MK-6194

PROTOCOL/AMENDMENT NO.: 008-04

Laboratory Assessments	Parameters
Assessments Other Screening Tests	 Coagulation: PT and INR, aPTT FSH (as needed in WONCBP only) Urine drug screen (to include at minimum: amphetamines, barbiturates, cocaine, opiates, cannabinoids and benzodiazepines) Alcohol test Serology (HIV antibody, HBsAg, HBsAb, HBcAb, and hepatitis C virus antibody) per site SOP Purified protein derivation (PPD test or QuantiFERON®-TB Gold test All study-required laboratory assessments will be performed by a central
	laboratory, except pregnancy tests, TB test, Urine Drug Screen (UDS), and alcohol test, which may be performed centrally or locally.

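### Exclusion 24 names hypomagnesemia, but no visible protocol-required test measures magnesium, so that limb cannot be checked systematically

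*Combined protocol and SAP*

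**What the plan says.** Exclusion 24, under the Diagnostic Assessments subheading of Section 5.2, has several limbs: QTc limits by sex, a history of risk factors for Torsades de Pointes, an electrolyte limb and QT-prolonging medication. The electrolyte limb excludes a person who "has uncorrected hypokalemia or hypomagnesemia". It gives no test, threshold or time for either electrolyte.

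Section 8.3.5 sends the reader to one list: "Refer to Appendix 2 for the list of clinical laboratory tests to be performed". That list is Table 7 in Appendix 2, headed "Protocol-required Safety Laboratory Assessments", and the appendix adds: "The tests detailed in Table 7 will be performed by the central laboratory". The chemistry row of the Schedule of Activities (Section 1.3) also points to Appendix 2.

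Two provisions let a site go beyond the list. Appendix 2 says: "Additional tests may be performed at any time during the study as determined necessary by the investigator or required by local regulations". Section 8 allows existing results, subject to protocol criteria and timing: "Procedures conducted as part of the participant's routine clinical management (eg, blood count) and obtained before signing of ICF may be used for screening".

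**The concern.** A mandatory exclusion that turns on a blood level normally has a matching required test. Here one of the two electrolytes in the same phrase has a test and the other does not. Section 8 expects the screening evaluations to confirm every eligibility criterion, and Section 5 allows no waivers, so sites are asked to confirm something for which the plan schedules no measurement.

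What is at stake is safety screening and even application of the criterion. The protocol itself lists low magnesium among QT-related risks. In a multi-site trial, one site may order the test for everyone, another may ask about history only, and a third may do neither. All three could consider themselves compliant.

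**Working it through.** No figure in the plan is in question, so the check is a comparison of passages.

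1. **Chemistry panel, Table 7.** BUN, potassium, AST, bilirubin, albumin, bicarbonate, chloride, phosphorous, creatinine, sodium, ALT, total protein, glucose, calcium, alkaline phosphatase, LDH, IgE and CRP. Potassium is present; magnesium is absent.

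2. **Rest of Table 7.** Hematology, urinalysis and pregnancy testing do not include magnesium. The Other Screening Tests row begins "Coagulation: PT and INR, aPTT FSH (as needed in WONCBP only) Urine drug screen" and goes on to alcohol, viral serology and TB. Magnesium is absent there too. The table shows no redaction marker.

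3. **Schedule of Activities.** No visible row names magnesium.

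4. **Comparison with other criteria.** Viral serology (exclusion 13), the drug screen (exclusion 27), TB (inclusion 11), pregnancy (inclusion 8) and potassium (exclusion 24) each have a matching entry in Table 7. Among the visible criteria that name a specific laboratory finding, magnesium is the one without an entry.

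5. **Wording of the criterion.** The plan marks known or historical conditions where it means them: exclusion 1 speaks of known hypersensitivity, and the Torsades limb of exclusion 24 of a history. The electrolyte limb is in the present tense and sits under a diagnostic subheading. It reads as a current finding, not as something to be taken from history.

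6. **Appendix 10.** Rule A lets a participant enter once all protocol-specified laboratory values are normal. Rule B excludes when such a value breaches an eligibility limit. Magnesium is not a protocol-specified value, so Rule B cannot act on it, and Rule A can be satisfied with magnesium unmeasured.

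7. **Recording.** Under Section 8.3.5, a local result outside the protocol list must go into the CRF if it changes management or is judged clinically significant. That rule does not require a normal discretionary magnesium result to be recorded, so the data may not show who was checked.

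8. **Illustrative size.** Inputs: at most 72 participants (Synopsis, Section 1.1) and an assumed prevalence of unrecognised low magnesium of 2% to 10%, which the documents do not supply. 72 × 0.02 = 1.4 and 72 × 0.10 = 7.2, so about 1 to 7 participants. The count is smaller if the expansion panels are reduced or cancelled, as Section 6.6 permits.

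**The case against.** The strongest reply is that the limb can still be used. Medical history is taken, qualifying routine results are accepted, extra tests are allowed at any time, and exclusions 2, 3, 7 and 28 let the investigator exclude for laboratory or safety concerns. All of that is true, and a known case of low magnesium can be excluded. But each route depends on prior knowledge or on discretion, so none ensures that every participant is checked.

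The plan also limits the consequences. QTc is itself an exclusion limb at screening and at predose Day 1, ECGs are scheduled at every visit, and Section 8.3.4 sets actions for a QTc increase of 60 msec or a value of 500 msec. These safeguards stand, and they keep the point modest.

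A reader might go further and infer that unmeasured magnesium confounds any QTc change attributed to MK-6194. The documents do not support that. Assignment is randomized against placebo, so pre-existing low magnesium is independent of assignment in expectation. Chance imbalance in small panels remains possible but is not systematic. QTc change is taken from each participant's own baseline, the median of triplicate predose ECGs. QTc is not a named primary endpoint; those are AEs and discontinuation from dosing due to AEs.

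The public text has limits. Some Schedule of Activities rows are redacted, exclusion 16 is not visible, and Appendix 8 is not available. A magnesium test elsewhere cannot be ruled out entirely, but Table 7, the stated list, appears intact.

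**Conclusion.** The mismatch is real and narrow. Of the two electrolytes in exclusion 24, one can be verified from required tests and the other cannot. A participant with unrecognised low magnesium may be enrolled, and the limb would be applied unevenly across sites.

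Two stronger statements are tempting and not supported. One is that exclusion 24 as a whole cannot be applied: its QTc, Torsades-risk, potassium and medication limbs all can be, from planned ECGs, history, chemistry and medication review. The other is that sites will enrol such participants: that depends on a prevalence the documents do not give, so only *may* is justified.

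The range of 1 to 7 of 72 rests wholly on the assumed 2% to 10%, and the conclusion does not depend on it. Sample size, power and error rates are unaffected. The conclusion assumes that Table 7, as published, is the complete list of required laboratory tests.

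**What to change.** Reconcile exclusion 24 with Table 7 in one of two ways.

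- **Preferred:** add serum magnesium to the Other Screening Tests row of Table 7, with a matching screening-only entry in the Schedule of Activities, and state what counts as low, for instance by the central laboratory's reference range. Without a stated definition, an added analyte would not make the criterion uniform. The Chemistry row is the wrong place for a screening-only test: chemistry is scheduled at 15 visits (screening, 13 visits from Day 1 to Day 141, and Day 169), so the test would be added at all of them.
- **Alternative:** reword the limb to say how it is ascertained, for example as known hypomagnesemia. This also removes the contradiction, but unrecognised cases stay undetected.

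Either is a short text edit. The first costs a small laboratory fee and possibly a few more screen failures. Chemistry is already drawn at screening, so an extra draw may not be needed, but whether that sample suffices should be confirmed against Appendix 8 and the laboratory manual.
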